3.2 Study Outcome Measures

Primary (safety) endpoint: The procedure is deemed safe if

- 1) **None** of the following unacceptable events occur within 7 days of fetal embolization:
 - a) Fetal death
 - b) Fetal intracranial hemorrhage, either parenchymal or extra-axial, other than petechial hemorrhage. A petechial hemorrhage is seen as focal staining of the brain parenchyma by blood products on MRI, is not associated with mass effect, and there are minimal neurologic sequelae. Petechial hemorrhages are usually considered non-serious adverse events in trials.
 - c) Maternal death
- 2) **None** of the following unacceptable events occur between fetal embolization and delivery:
 - a) Intra-procedural and post-procedural morbidity to the fetus and mother, probably related to the fetal intervention, e.g. placental abruption with subsequent sequelae
 - b) Preterm delivery < 28 weeks, probably related to the fetal intervention
 - c) Maternal blood transfusion or unanticipated surgical intervention, probably related to the fetal intervention
 - d) Presence of fetal imaging evidence of new brain injury in a location or pattern unexpected for the natural history of vein of Galen malformation, probably related to the fetal intervention

Secondary (efficacy) endpoint: The procedure is deemed efficacious if **none** of the following serious postnatal events occur within 30 days of birth:

1. Urgent neonatal embolization is needed. Without fetal intervention, we'd expect 80% of the cohort to require such intervention.
2. Neonatal death. Without fetal intervention, we'd expect a mortality rate of 40% in this cohort.
3. Brain MRI within the first three weeks after birth reveals parenchymal brain injury (acute infarct or gliosis) affecting > 10% of the supratentorial brain volume. Without fetal intervention, we'd expect 30% of patients in this cohort to show this kind of injury.

Additional efficacy data to be collected includes assessment of the neurocognitive development in the treated cohort. Subjects will be followed and assessed until age 24 months and results will be compared to historical controls of NAR VOGM patients treated using the current neonatal paradigm.

Comparison of outcomes will be made with published (meta-analysis and UK national data [1, 2, 6, 7]) and institutional historical results for fetuses who receive standard neonatal or post-neonatal treatment.

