5.4 Subject Withdrawal

5.4.1 Reasons for Withdrawal

Subjects are free to withdraw from participation in the study at any time upon request.

An investigator may terminate a study subject's participation in the study if:

- Any clinical adverse event (AE), laboratory abnormality, or other medical condition or situation occurs such that continued participation in the study would not be in the best interest of the subject.
- The subject meets an exclusion criterion (either newly developed or not previously recognized) that precludes further study participation.

- Ideal fetal positioning for the procedure cannot be achieved over a duration of 40 minutes with epidural analgesia; a single, separate 40 minute attempt may be undertaken at > 24hrs after the first attempt.
- The fetal embolization procedure is attempted but unable to be completed for any reason.

5.4.2 *Handling of Subject Withdrawals*

Any subject withdrawn prior to completing the fetal embolization will be replaced. The enrollment goal of the study is to achieve a cohort of 20 evaluable participants who have completed the intervention.

All subjects enrolled in the study will plan to deliver at BWH. In the event that there is an unplanned delivery at an institution other than BWH, the subject will receive standard of care at the outside institution. We will be available for consultation and, as is the case for non-research subjects, would consider the benefits and risks of transfer to BCH versus local treatment, depending on the clinical severity of the neonate. All advice will be purely based on the best medical interest of the baby, and not the research study. We will attempt to collect all relevant clinical information from the outside institution.

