7.4 Delivery

Plans will be made for all subjects to be delivered at BWH. The mode of delivery is not impacted by the fetal intervention and will be determined based on clinical criteria. Likewise, gestational age of delivery will be determined clinically. Depending on the specifics of each case, including how far along the pregnancy is, how severely affected the fetus is, and other factors, in some cases, early delivery would be the chosen option, while in others, termination might be the recommended option, as previously discussed by the subject with the clinical care team. A recommendation of termination of pregnancy would result from major cerebral injury (intracranial hemorrhage other than petechial or parenchymal infarct >10% of the supratentorial brain volume) visualized on fetal imaging, in the setting of a gestational age young enough that termination remains an option. As such major cerebral injury is one of the unacceptable safety events mentioned above in Section 3.2 and below in Section 11.3, the subject in question would be included in the calculations related to the two-stage study design for safety. However, since fetal death would not have been spontaneous but rather by termination of pregnancy, the subject would not be counted towards the fetal deaths in the study.

If no such situation arises, elective delivery will be performed on a date chosen by the obstetrician as optimal in terms of safety for the mother and baby, in the same way that delivery dates are chosen for patients with vein of Galen malformations who do not undergo fetal intervention.

The newborn will be admitted to the NICU, as per the current practice for all patients with VOGM. As per clinical care, an MRI and echocardiogram will be performed as soon as possible after delivery, typically on day 1 of postnatal life. All care, including additional embolization procedures and additional imaging, will be done per standard of care for this patient population. Per our protocol (and similar to that of most major referral centers for VOGM), if a neonatal patient is unable to be extubated or is not stable enough on medications to be discharged from the NICU within a week due to cardiopulmonary failure, this indicates a need for urgent neonatal embolization.

At our center, extubation criteria in neonates without an underlying lung disease include:

- Patient awake with spontaneous and regular breaths, and
- Mean airway pressure on the ventilator < 10 cmH₂O and FiO₂ < 0.25

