11.3 Safety Review

Two-stage design for safety endpoint

In Stage 1, up to 11 evaluable patients will be enrolled (**Table 2**). Out of 11 patients, if 3 or more patients experience an unacceptable event (see definition in Section 3.2 above and recapitulated below Table 2), the intervention is unsafe and not worthy of further study. If 2 or fewer experience any unacceptable event, the trial will proceed to Stage 2, where an additional 9 evaluable patients will be enrolled, for a total of $N=20$ evaluable patients. Out of $N=20$ patients, if 4 or more patients experience any unacceptable event, the intervention is unsafe and not worthy of further study. If 3 or fewer patients experience any unacceptable event, the intervention is sufficiently safe and worthy of further study. In addition, in case of a single maternal death, the study will be halted pending review by the DSMB and the FDA.

This design tests the null hypothesis that the rate of unacceptable events is $P > 30\%$ versus the alternative that $P < 5\%$. The total type I error rate is 0.097 and the power is 97.5%. If the intervention is truly unsafe, there is a 68.7% probability of early trial termination.

Table 2: Decision rules for safety based on the optimum two-stage design.

	Cumulative number of patients with unacceptable events	Decision
Stage 1: Enroll 11 patients	3 or more	Terminate the trial: agent not worthy of further study
	2 or fewer	Inconclusive result: proceed to Stage 2
Stage 2: Enroll 9 additional patients	4 or more	Terminate the trial: agent not worthy of further study
	3 or fewer	Trial concludes: agent worthy of further study

- 1) Unacceptable events within 7 days of fetal embolization include:
 - a) Fetal death
 - b) Fetal intracranial hemorrhage, either parenchymal or extra-axial, other than petechial hemorrhage. A petechial hemorrhage is seen as focal staining of the brain parenchyma by blood products on MRI, is not associated with mass effect, and there are minimal neurologic sequelae. Petechial hemorrhages are usually considered non-serious adverse events in trials.
 - c) Maternal death
- 2) Unacceptable events occur between fetal embolization and delivery include:
 - a) Intra-procedural and post-procedural morbidity to the fetus and mother, probably related to the fetal intervention, e.g. placental abruption with subsequent sequelae
 - b) Preterm delivery < 28 weeks, probably related to the fetal intervention

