11.4 Efficacy Review

Two-stage design for efficacy endpoint

In Stage 1, up to 11 evaluable patients will be enrolled (**Table 3**). Out of 11 patients, if 5 or fewer patients respond, i.e. do not experience a serious postnatal event (see definition in Section 3.2 above), the intervention is not efficacious and not worthy of further study. If 6 or more respond, the trial will proceed to Stage 2, where an additional 9 evaluable patients will be enrolled, for a total of N=20 evaluable patients. Out of N=20 patients, if 10 or fewer patients respond, the intervention is not sufficiently efficacious and not worthy of further study. If 11 or more patients respond, the intervention is sufficiently efficacious and worthy of further study.

This design tests the null hypothesis that the response rate is $P \leq 40\%$ versus the alternative that $P \geq 70\%$. The total type I error rate is 0.099 and the power is 90.2%. If the intervention is truly not efficacious, there is a 75.3% probability of early trial termination.

Table 3: Decision rules for efficacy based on the optimum two-stage design.

	Cumulative number of responses	Cumulative number of non-responders (patients with serious postnatal events)	Decision
Stage 1: Enroll 11 patients	5 or fewer	6 or more	Terminate the trial: fetal intervention not worthy of further study
	6 or more	5 or fewer	Inconclusive result: proceed to Stage 2
Stage 2: Enroll 9 additional patients	10 or fewer	10 or more	Terminate the trial: fetal intervention not worthy of further study
	11 or more	9 or fewer	Trial concludes: fetal intervention worthy of further study

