11.5 Timing of safety and efficacy rules

The safety endpoint is observed from Day 0 (the day of fetal intervention) to Day 7 post-intervention. The efficacy endpoint is observed from the birth to Day 30 of life. Both safety and efficacy decision rules must be satisfied before enrollment to Stage 2 is allowed. Prior to initiating accrual at Stage 2, a sensitivity analysis will be performed to determine if both the safety and efficacy rules would be triggered. Hence, trial enrollment for Stage 2 may be suspended after the enrollment of the 11th patient to allow observation up to Day 30 of life of the most recently treated patient.

The safety and efficacy rules are to be interpreted as specifying that the trial will stop as soon as either criterion is reached; e.g., if the first 3 evaluable patients experience unacceptable prenatal events (safety rule), or the first 6 patients experience serious postnatal events (efficacy rule), then the trial stops immediately. Beyond the 11th patient, the trial halts as soon as 4 unacceptable prenatal events or 10 serious postnatal events occur.

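### The efficacy rule counts only postnatal events, so a treated pregnancy lost before birth would, as written, be scored as a response

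*Combined protocol and SAP*

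**What the plan says.** **Termination (Section 7.4).** Major cerebral injury on fetal imaging, at a gestation where termination is still possible, leads to a recommendation to terminate. For safety, "the subject in question would be included in the calculations related to the two-stage study design for safety". Because the death is not spontaneous, "the subject would not be counted towards the fetal deaths in the study".

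**Efficacy endpoint (Section 3.2).** The procedure is efficacious if none of the "following serious postnatal events occur within 30 days of birth". The three events are urgent neonatal embolization, neonatal death, and injury to more than 10% of the supratentorial brain on MRI after birth. All need a live birth.

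**Efficacy rule (Section 11.4).** The intervention fails Stage 1 "if 5 or fewer patients respond, i.e. do not experience a serious postnatal event". Table 3 labels non-responders as the patients with serious postnatal events, and its two columns add up to all 11 and all 20 subjects. There is no third category.

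**Who is in the 11 and the 20 (Section 5.4.2).** The target is "a cohort of 20 evaluable participants who have completed the intervention". Only subjects withdrawn before completing embolization are replaced.

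**Role of the rule (Section 11.5).** "Both safety and efficacy decision rules must be satisfied before enrollment to Stage 2 is allowed". The trial also stops once 6 serious postnatal events (Stage 1) or 10 (overall) have occurred. Efficacy is observed from birth to Day 30 of life.

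**The concern.** A subject who has completed embolization stays in the denominator. If the pregnancy then ends before live birth, none of the three failure events can happen. Under the wording of Section 11.4 and Table 3 the subject falls in the responder column, and the worst fetal outcome helps the intervention to pass. The gap covers spontaneous fetal death as well as termination.

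Efficacy is the secondary objective, but its rule controls entry to Stage 2, early stopping and the final efficacy conclusion. With 20 subjects, one to three losses can decide it. If the plan is silent, the status of those subjects would have to be settled after their outcomes are known.

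**Working it through.** **1. The plan's own figures.** Efficacy passes with at least 6 of 11 and at least 11 of 20 responses (Section 11.4):

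P(pass; p) = Σ over x = 6 to 11 of C(11,x) pˣ (1−p)¹¹⁻ˣ × P[Bin(9,p) ≥ 11−x]

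- p = 0.40: 0.0990 (plan: 0.099)
- p = 0.70: 0.9020 (plan: 90.2%)
- early stop at p = 0.40, P[Bin(11, 0.40) ≤ 5]: 0.7535 (plan: 75.3%)

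Safety passes with at most 2 of 11 and at most 3 of 20 unacceptable events (Section 11.3). By the same method this gives 0.0967 at a 30% event rate and 0.9755 at 5% (plan: 0.097 and 97.5%). The design arithmetic is right; the gap is in the endpoint definition.

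**2. A worked case.** Three losses can still pass safety, provided at most 2 fall in Stage 1: "If 3 or fewer patients experience any unacceptable event, the intervention is sufficiently safe and worthy of further study".

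- Stage 1: 2 losses and 9 live births, 6 of whom respond.
- Stage 2: 1 loss and 8 live births, 2 of whom respond.
- Total: 8 responders among 17 live births, plus 3 losses. Serious postnatal events: 17 − 8 = 9, below the limit of 10.

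As written, responses are 8 + 3 = 11 of 20 and the intervention passes. With losses as non-responses there are 8 of 20, that is 9 + 3 = 12 non-responders, and it fails.

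**3. Chance of passing both rules.** Each treated subject is terminated with probability t, truly responds with probability 0.40, or does neither with probability 0.60 − t. Each termination is a safety event and there are no others. The probability is the trinomial sum over Stage 1 (11 subjects) and Stage 2 (9 subjects) of outcomes that meet both rules. The values of t are assumptions.

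| t | Losses scored as responses | Losses scored as non-responses |
|---|---|---|
| 0.05 | 0.188 | 0.098 |
| 0.10 | 0.251 | 0.094 |

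If other safety events also occur independently at 5% in the remaining subjects, the figures are 0.155 against 0.090 (t = 0.05) and 0.178 against 0.078 (t = 0.10). The safety rule narrows the difference but does not remove it.

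**4. The reading in between.** If losses were treated as not observed and replaced, the response rate under test would be 0.40/0.95 = 0.421 or 0.40/0.90 = 0.444. The efficacy rule alone would then pass with probability 0.136 or 0.186, against 0.099 with losses as non-responses.

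**5. Power cost of the fix.** If 70% of live-born subjects respond and losses are failures, response among treated subjects is 0.70 × 0.95 = 0.665 or 0.70 × 0.90 = 0.630. Efficacy power falls from 0.902 to 0.838 or 0.753.

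**The case against.** The strongest reply is that the responder reading was never meant. Section 11.5 observes efficacy from birth, so a pregnancy without a live birth has no observation window and could be called not observed. That reading is available, but it does not settle the matter. Section 5.4.2 provides no replacement after a completed embolization, and Table 3 has no column for unobserved subjects.

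A second reply is that the safety rule catches these cases. In part it does: it limits losses that count as safety events to three in a trial that passes. It does not limit every loss. A spontaneous fetal death after Day 7 that is not judged probably related to the intervention is not on the Section 3.2 list.

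Third, the loss rates are assumed, and the true number of terminations may be zero. That stands. So does a point of labelling: the higher probabilities are not a wrong type I error for the test as specified. Scoring losses as responses moves the tested rate from 40% to 45% or 50%, so the figures show a change in what is being measured.

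A reader might go further and infer from "the subject would not be counted towards the fetal deaths in the study" that the plan hides deaths or weakens the primary safety decision. The documents do not support this. Section 7.4 puts the same subject in the safety rule, any death is a serious adverse event (Section 8.1.2), and all such events go to the DSMB (Sections 8.4 and 9). No fetal-mortality analysis is planned that the label would alter.

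**Conclusion.** The point holds for the secondary efficacy endpoint. As written, a treated pregnancy lost before live birth adds to the responses and cannot add to the stopping count. This is probably an oversight, and a not-observed reading is also possible, but no text makes the subject a non-responder.

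The effect can decide the result: the same data give 11 of 20 or 8 of 20. At assumed termination rates of 5% or 10%, with 40% true response among all treated subjects and no other safety events, the chance of passing both rules is about 1.9 or 2.7 times what it is with losses as failures (0.188/0.098 and 0.251/0.094). With no losses there is no effect.

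The exclusion of terminations from the fetal deaths is a reporting choice, stated openly, and not an error in the decision rules. Label: cheap improvement.

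**What to change.** Add to Sections 3.2 and 11.4, and reflect in the non-responder column of Table 3:

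*A treated subject whose pregnancy ends before live birth, by fetal death or termination, counts as a non-responder and toward the efficacy stopping count.*

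Sample size, thresholds and data collection do not change, and the stated type I error of 0.099 then applies to response among all treated subjects. The cost is the loss of power shown above, and that some losses due to the natural history of the malformation will count as failures. The investigators should accept both knowingly.

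Two further changes are optional:

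- Report spontaneous fetal deaths, terminations and their total side by side, over all treated subjects. The two-center fetal series cited in Section 2.1.1 gives late termination and intrauterine death as one 33% figure, so the total is the closer comparison.
- Align Section 7.4 with Section 3.2. Section 7.4 treats major cerebral injury as an unacceptable event without qualification. Section 3.2 counts hemorrhage outright only within 7 days, and later "new brain injury in a location or pattern unexpected for the natural history of vein of Galen malformation, probably related to the fetal intervention". Widening Section 3.2 to match would change the primary endpoint and is not proposed here.

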7.5 Follow up Visits

All neonatal subjects will be followed for 2 years post-birth. Families will be contacted by a study investigator every 6 months, \pm 1 month, in order to collect information about the neurological and overall developmental status. If the patients undergo cardiology evaluations as part of their clinical care, the clinical information from these evaluations will be collected as well. Since many subjects are expected to reside a long distance from Boston Children's Hospital and will not be able to attend in-person follow up visits every 6 months, the assessment of neurodevelopmental and health status is designed to be conducted by telephone as needed. The following neurodevelopmental assessment tools will be used according to the schedule outlined below:

1. Vineland Adaptive Behavior Scales for assessment of overall development in the four major domains of neurologic function (communication, motor, socialization and daily living skills)
2. REEL (Receptive-Expressive Emergent Language Test) for more in depth evaluation of language skills
3. Child Behavior Checklist (CBCL) to assess emotional and behavioral function
4. DAYC-2 cognitive assessment: The Development Assessment of Young Children-Second Edition (DAYC-2). The DAYC-2 Cognitive domain will be used to assess cognitive development in infant at 18 and 24 months.
5. Bayley examination (in-person only): The Bayley Scales of Infant and Toddler Development is an assessment instrument designed to measure physical, motor, sensory, and cognitive development in babies and young children. It involves interaction between the child and examiner and observations in a series of tasks.

Visit 3: 6 month visit (\pm 1 month):

- Ask families about developmental milestones, any early interventions, and incidence of seizures/epilepsy and their treatment
- Vineland Adaptive Behavior Scales
- REEL

Visit 4: 12 month visit (\pm 1 month):

- Ask families about developmental milestones, any early interventions, and incidence of seizures/epilepsy and their treatment
- Vineland Adaptive Behavior Scales
- REEL

Visit 5: 18 month visit (\pm 1 month):

- Ask families about developmental milestones, any early interventions, and incidence of seizures/epilepsy and their treatment
- Vineland Adaptive Behavior Scales
- REEL
- Child Behavior Checklist
- DAYC-2 cognitive assessment
- Bayley examination (if in-person)

Visit 6: 24 month visit (\pm 1 month):

- Ask families about developmental milestones, any early interventions, and incidence of seizures/epilepsy and their treatment
- Vineland Adaptive Behavior Scales
- REEL
- Child Behavior Checklist
- DAYC-2 cognitive assessment
- Bayley examination (if in-person)

8 ASSESSMENT OF SAFETY

8.1 Specification of Safety Parameters

All adverse events of Grade 2 or higher that occur in mothers, fetuses, or neonates and which could plausibly be related to the procedure, based on their nature or temporal relationship to the procedure, will be recorded. The occurrence of events will be assessed during the procedure, at the time of hospital discharge, at each follow-up visit (including imaging results), at delivery/birth, while the neonate is inpatient, and at discharge from the NICU. All subjects will be questioned for adverse events at the time of their follow-up studies (see above) or fetal or neonatal demise. The data collected will be recorded using an Adverse Event form, which will record a description of the event, time of onset in relation to the procedure, the severity of the adverse event, the treatment required, and the outcome.

Preliminary classification of adverse events will be made by the obstetrician for the mother and by the neurointerventionalist for the fetus/neonate. All events will be subsequently reviewed by the DSMB.

Adverse events will be classified as occurring in the mother, or the fetus/neonate, and as most plausibly related to one of the following, based on timing and physiology:

- a) Maternal anesthesia
- b) Fetal positioning or manipulation
- c) Fetal paralysis or analgesia
- d) Needle passage through maternal abdomen, uterus, or placenta
- e) Needle passage into the fetal cranium or other fetal structures
- f) Microcatheter/microwire navigation from the fetal torcular to the prosencephalic varix
- g) Coil deployment within the prosencephalic varix
- h) Needle withdrawal
- i) Other
- j) Unknown

8.1.1 ***Adverse Events***

An adverse event is any untoward or unfavorable medical occurrence in a human subject, including any abnormal sign (for example, abnormal physical exam or laboratory finding), symptom, or disease, temporally associated with the subject's participation in the research, whether or not considered related to the subject's participation in the research.

8.1.2 ***Serious Adverse Events***

A serious adverse event, including a serious suspected adverse reaction or serious adverse reaction as determined by the Investigator or the sponsor is any event that results in any of the following outcomes:

1. Death. This includes any death that occurs during the conduct of a clinical study, including deaths that appear to be completely unrelated to the intervention (e.g., a car accident). If a study subject dies during the study and an autopsy is performed,

the autopsy results will be attached to the study subject's Case Report Form (CRF). Possible evidence of organ injury and the potential relationship of the injury to the intervention are of particular interest. The autopsy report should distinguish the relationship between the underlying diseases, their side effects, and the cause of death.

2. Life-threatening. This includes any AE during which the study subject is, in the view of the investigator, at immediate risk of death from the reaction as it occurred. This definition does not include any event that may have caused death if it had occurred in a more serious form.
3. Persistent or significant disability or incapacity or substantial disruption of the ability to conduct normal life functions.
4. Inpatient hospitalization or prolongation of existing hospitalization beyond the expectation for delivery, except for admission for elective surgery.
5. Important medical event that may not result in one of the above outcomes, but which may jeopardize the health of the study subject or require medical or surgical intervention to prevent one of the outcomes listed in the above definition of serious event.

It is anticipated that all neonatal subjects on this study, as patients with vein of Galen malformations, will be hospitalized during the course of treatment. Therefore, regarding the hospitalization criterion for seriousness, only AEs that clearly result in the *prolongation* of hospitalization, not related to typical NICU events (e.g. reintubation, poor feeding, apnea of prematurity, etc.) or which are life-threatening should be considered serious for this study.

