2.4 Potential Risks and Benefits

2.4.1 Potential Risks

Risks to the mother include the following:

- Hemorrhage requiring blood transfusion and/or further surgery due to injury of the abdomen, uterus, placenta, and umbilical cord
- Damage to other maternal organs (bladder, bowel) requiring observation, additional surgery
- Placental abruption
 - in certain cases of maternal vascular compromise due to abruption, a hysterotomy, cesarean section and/or hysterectomy may be required, which would impact future reproductive ability
- Death
- Allergic reaction

- Spinal anesthesia risks
- Chorioamniotic separation
- Premature labor /delivery: associated maternal risks of treatment
- Premature rupture of membranes
- Infection

Risks to the fetus include the following:

Risks related to undergoing a fetal procedure:

- Preterm delivery with gestational age associated risks
- Procedure-related fetal death
- Stillbirth
- Fetal paralysis
- Intravascular absorption of narcotic, atropine, or muscle paralytic medication
- Hemorrhage and/or injury of fetal structures, placenta, and umbilical cord
- Foreign body retention
- Infection

Risks related to embolization:

- Intracranial hemorrhage
- Seizures, epilepsy, or other neurological disorders
- Vessel dissection or perforation
- Allergic reaction
- Non-target embolization of the coil
- Brain ischemia
- Inadvertent vessel thrombosis or occlusion

There is no expected radiation risk, as the procedure will be performed under ultrasonographic guidance.

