9 STUDY OVERSIGHT

In addition to the PI's responsibility for oversight, study oversight will be under the direction of a Data and Safety Monitoring Board (DSMB) composed of five senior faculty of medical schools not affiliated with the study. Members will have expertise in pediatric neurointerventions, management of vein of Galen malformations, neonatology, maternal-fetal medicine, and fetal/neonatal cardiology. The DSMB will meet as outlined in the DSMB charter.

The DSMB will make recommendations to the PI and the Institutional Review Boards at Boston Children's Hospital and the Brigham and Women's Hospital about protocol changes necessary to protect the scientific validity of the study or to protect study participants, including study termination. The DSMB will meet by phone or video conference at least twice a year after the start of patient enrollment to review all procedures. All serious adverse events will result in notification of the DSMB, which will evaluate the severity of the event, the relationship to the study intervention, and whether stoppage criteria have been met. The DSMB charter indicates additional time points when a DSMB meeting may need to be convened for evaluation of continuation of the study.

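### Section 8.1.2 exempts prolonged neonatal stays from typical NICU events whatever their cause, so a long stay after a procedure-related preterm birth at 28 weeks or later can lose SAE status

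*Combined protocol and SAP*

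**What the plan says.** Section 8.1.2 lists five criteria for a serious adverse event: death, life-threatening event, lasting disability, hospitalization or its prolongation, and important medical event. It then notes that every neonate in the trial will be hospitalized anyway, and restricts the fourth criterion: "regarding the hospitalization criterion for seriousness, only AEs that clearly result in the" prolongation of the stay, "not related to typical NICU events (e.g. reintubation, poor feeding, apnea of prematurity, etc".), "or which are life-threatening should be considered serious for this study". The list of typical events is open-ended, and nothing in the sentence separates events caused by the procedure from others.

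Section 2.4.1 places "Preterm delivery with gestational age associated risks" among the risks of undergoing a fetal procedure.

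Section 3.2, repeated in Section 11.3, counts preterm delivery as an unacceptable safety event only before 28 weeks and only if probably related to the intervention. That group of events is observed up to delivery.

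Seriousness sets the reporting route. Under Section 9, "All serious adverse events will result in notification of the DSMB", and the board then considers severity, relationship and the stopping criteria. Section 8.4 adds prompt IRB reporting of SAEs and sends all other adverse events to the DSMB at regular intervals.

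**The concern.** The main purpose of this trial is prenatal safety, and Section 2.3 states that no clinical study of fetal embolization for this malformation exists. Preterm birth is a foreseeable harm of the procedure by the plan's own account. Its usual neonatal consequences, such as apnea of prematurity and poor feeding, are among the events that the exemption names.

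Because the exemption ignores cause, it treats two infants alike: one whose prematurity has nothing to do with the trial, and one who was born early because of the needle procedure. For the second infant, a longer NICU stay is a procedure harm. Under the fourth criterion as restricted, that stay does not make the event serious.

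At stake are the speed of review and the content of the neonatal SAE table. A cluster of such stays would reach the DSMB through periodic review rather than case by case, and the IRB would not receive them promptly as SAEs.

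**Working it through.** No figure in the plan is in dispute here, so the check follows one case through the rules. The case is a treated fetus delivered preterm at 28 weeks or later, with the birth judged related to the procedure. The infant then has apnea of prematurity and poor feeding that are not life-threatening but lengthen the NICU stay.

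1. **Can the case arise?** Section 5.1 admits fetuses from 23 weeks to term, and Section 2.4.1 names preterm delivery as a procedure risk. Yes.
2. **Would these events lengthen the stay?** The NICU discharge criteria in Section 7.4 require good feeding and freedom from breathing difficulty. Yes.
3. **Serious under criterion 4?** Prolongation would ordinarily qualify, but the neonatal paragraph removes these events by name. No.
4. **Serious under another criterion?** Criteria 1 and 2 are not met by construction. Criterion 3 (lasting disability) may or may not be. Criterion 5 covers events that "may jeopardize the health of the study subject or require medical or surgical intervention to prevent one of the outcomes" in the list, so it could apply, but only by case-level judgment.
5. **A primary safety event?** The preterm-delivery item is not met, because birth was not before 28 weeks. The other items in that group run only to delivery, and apnea and poor feeding arise after it. The general morbidity item might be stretched to cover the birth itself, but a separate preterm item with its own cut-off suggests that later births were not meant to count.
6. **Recorded at all?** Yes, if Grade 2 or higher and plausibly related (Section 8.1). Section 8.2 runs recording through NICU discharge.
7. **Which route?**

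| Status | DSMB | IRB |
|---|---|---|
| SAE | notified for each event (Sections 8.4 and 9) | prompt report (Section 8.4) |
| Other AE | review at regular intervals (Section 8.4); meetings at least twice a year (Section 9) | prompt only if it is an unanticipated problem (Section 8.4) |

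Unless criterion 3 or 5 is invoked, the case follows the second row.

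**Effect on the decision rules.** Sections 11.3 and 11.4 count the events defined in Section 3.2, not SAEs. With X ~ Bin(11, p) and Y ~ Bin(9, p), the plan's figures are reproduced:

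- Safety: P(declared safe) = Σ P(X = x)·P(Y ≤ 3 − x) over x = 0 to 2. At p = 0.30 this is 0.0967 (plan 0.097); at p = 0.05 it is 0.9755 (plan 97.5%). Early stopping, P(X ≥ 3) at p = 0.30, is 0.6873 (plan 68.7%).
- Efficacy: P(declared efficacious) = Σ P(X = x)·P(Y ≥ 11 − x) over x = 6 to 11. At p = 0.40 this is 0.0990 (plan 0.099); at p = 0.70 it is 0.9020 (plan 90.2%). Early stopping, P(X ≤ 5) at p = 0.40, is 0.7535 (plan 75.3%).

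Seriousness enters none of these formulas, so changing the exemption leaves every figure as it is.

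**The case against.** The case for leaving the text alone is respectable. All these infants will be in the NICU, and without some filter routine events would flood the SAE listing. The plan gives that reason openly. The exemption opens by limiting itself to the hospitalization criterion, and it keeps life-threatening events. Events with a plausible link to the procedure are recorded from Grade 2 upward, and Section 8.1 says that the DSMB will review all events. Probably related births before 28 weeks already count towards the safety stopping rule. All of this stands, and it limits the point to the route and speed of reporting for a subset of events.

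It can also be said that seriousness and relatedness are separate judgments, and that the fix mixes them. That is fair as a matter of form. But criterion 4 itself carries no condition on cause. The exemption departs from it by event type, and the fix only narrows that departure.

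Two stronger readings are tempting and should be resisted.

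- **That these harms are not reported as SAEs at all.** The closing words of the exemption are loose enough to suggest it. However, the sentence begins by confining itself to one criterion, and criteria 1, 2, 3 and 5 are never withdrawn. A reintubation can still be serious under criterion 2 or 5.
- **That the plan hides treatment failure.** Section 7.4 treats a neonate "unable to be extubated or is not stable enough on medications to be discharged from the NICU within a week due to cardiopulmonary failure" as needing urgent embolization, while Section 8.1.2 calls reintubation typical. Failed extubation and reintubation overlap but are not the same. When cardiopulmonary failure leads to urgent embolization within 30 days of birth, it counts as a non-response in the secondary endpoint. It then feeds the stopping rule (6 serious postnatal events in Stage 1, 10 overall) whatever its SAE label.

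**Conclusion.** The point holds in a limited form. A non-life-threatening prolonged stay from a named NICU event, after a procedure-related preterm birth at 28 weeks or later, can lose SAE status under criterion 4 and is not caught by the preterm item of the primary endpoint. What is lost is event-by-event DSMB notification, prompt IRB reporting as an SAE, and a place in the SAE table. The event does not disappear from the trial record.

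The conclusion rests on reading the exemption as written, with no implied condition on cause, and on nobody invoking criterion 3 or 5 for the event.

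The number of infants affected cannot be given. A reader might try to derive one by applying an assumed preterm rate, the 30% NAR target in Section 11.2, or the efficacy null to 20 infants. The documents support none of these. They state no preterm or reintubation rate, NAR status is not reintubation, and non-response also includes death and MRI injury. The only bound available is the treated cohort of about 20. No endpoint, stopping rule or error rate changes. This is a cheap improvement to safety reporting, not a flaw in the trial's inference.

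**What to change.** Add one sentence to Section 8.1.2: the exemption for typical NICU events does not apply when the event, or the preterm birth that led to it, is judged at least possibly related to the fetal intervention, using the Possible, Probable and Definite categories of Section 8.3.1. Routine events in infants whose prematurity is judged unrelated stay exempt.

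The exemption should not be lifted for every event due to cardiopulmonary failure. That is the expected course of the disease in part of this cohort, the efficacy rule already captures it when it leads to urgent embolization, and the extra reporting would be a debatable trade-off. Stating that criteria 1, 2, 3 and 5 apply to neonates unchanged, and closing the open-ended list, would be useful clarification but is optional.

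The cost is a few more SAE reports. Timing is one of the Section 8.3.1 guidelines, so some preterm births will be called possibly related on timing alone. With about 20 treated infants that burden is small. The two-stage rules and the sample size stay as they are.
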